Sleep = 9 hours, permit 2 hours charging = 7 hours. 60% of 7 hours = 252 mins, 4.2 hours. Exclude data point if active night + sedentary night = <4.2 hours

Night time rest endpoints

Sleep = 9 hours, permit 2 hours charging = 7 hours. 60% of 7 hours = 252 mins, 4.2 hours. Exclude data point if active night + sedentary night = <4.2 hours

Heart Rate Variability (24 hour endpoints only)

The amount of data present over a 24-hour recording period is also important for the 24 hour endpoints for HRV: mean and variance for HRV recorded using RMSSD methods (24 hours). 24-hour RMSSD HRV data with 40% or more data present will be accepted for analysis. The number of time windows that the HRV data is determined from is recorded in the dataset from McLaren. The following data quality rule will be applied:

Number of 5-minute windows (number of data points) in 24 hrs = 288. Allow for 2 hours charging = 24. Leaves 264 data points. Ruling = require 40% or more of data present for the 24-hour time period, otherwise it is not considered as representative of 24 hours. 40% of 264 = 105.6. Therefore, exclude data point if number of 5-minute window (number of data point) < 105.

Speech Endpoints

There is no data quality rule for Speech data as there are no data quality deviators, and all available data will be included in the summary and statistical analysis.

The data quality deviator flags will be populated in the data and the summary tables and figures will be produced for data with the deviator and without the data quality deviator.

[Table 3](#) provides an overview of the planned efficacy analyses, with further details of data displays being presented in [Appendix 11](#): List of Data Displays.

Table 3 Overview of Planned Exploratory Analyses

Endpoint / Parameter/ Display Type	Absolute						Change from Baseline							
	Stats Analysis			Summary		Individual	Stats Analysis			Summary		Individual		
	T	F	L	T	F[1]	F	L	T	F	L	T	F[1]	F	L
Actigraphy - feasibility & Wear time Measures														
Wear Time (active + sedentary time)				Y			Y							
Duration of day time wear time				Y			Y							
Duration of night time wear time				Y			Y							
Actigraphy Diary Data – feasibility measures														
Actigraphy Diary data) (Items 2, 3, 5, 6, 8) And Feasibility				Y			Y							
Device impact Data – feasibility measures														
Device Impact				Y			Y							

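### The RMSSD cut-off of fewer than 105 windows accepts a recording that falls below the plan's own 40% minimum

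*SAP*

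**What the plan says.** SAP section 7.1.1, under the heading for 24-hour heart rate variability endpoints, states the criterion twice. The first statement is "24-hour RMSSD HRV data with 40% or more data present will be accepted for analysis". The second gives the reason: "Ruling = require 40% or more of data present for the 24-hour time period, otherwise it is not considered as representative of 24 hours".

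The section then turns the percentage into a count. It starts from "Number of 5-minute windows (number of data points) in 24 hrs = 288", makes a deduction for charging ("Allow for 2 hours charging = 24. Leaves 264 data points"), and obtains "40% of 264 = 105.6". From this it draws the operating rule: "Therefore, exclude data point if number of 5-minute window (number of data point) < 105".

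The SAP gives no other RMSSD cut-off and no rounding convention for this one, and it does not describe the 40% as approximate.

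**The concern.** The criterion is a minimum, and its exact value in windows is 105.6. Rounding a minimum down admits a value that fails it. The cut-off as written keeps a recording with 105 windows, which the sentence just before it treats as not representative of 24 hours.

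The cut-off matters because it defines which RMSSD data count as quality data. Section 7.1.1 gives no other quality rule for these endpoints. Section 7.1.2 restricts the statistical analysis to quality data. In Appendix 11 the flag therefore feeds:

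- the quality-data RMSSD summaries (Tables 2.110, 2.112, 2.114, 2.115, 2.121, 2.123, 2.125 and 2.126);
- the RMSSD and ALSFRS-R correlation tables (2.128, 2.130 and 2.132);
- the quality-data plots (Figures 2.68, 2.70, 2.74 and 2.76);
- Listings 60 and 63;
- the count of HRV deviators in Table 2.144.

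Someone who programs the percentage and someone who programs the integer would both be following section 7.1.1, yet they would flag a 105-window recording differently. A report saying that all analysed RMSSD data had at least 40% present could be untrue.

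**Working it through.** **Inputs, all from SAP section 7.1.1:** 5-minute windows, a 24-hour recording, 2 hours allowed for charging, a minimum share of 40%, and a cut-off that excludes counts below 105.

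**Step 1: reproduce the plan's figures.**

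- Windows in 24 hours: 24 × 60 / 5 = 288.
- Windows allowed for charging: 2 × 60 / 5 = 24.
- Windows available: 288 − 24 = 264.
- Minimum in windows: 0.40 × 264 = 105.6.

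All four agree with the SAP.

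**Step 2: find the smallest whole count that meets the criterion.** The count must be at least 105.6, so it must be at least 106.

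**Step 3: compare the written cut-off with the criterion around the threshold.**

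| Windows | Share of 264 | Meets 40%? | Under the cut-off of < 105 | Under a cut-off of < 106 |
|---|---|---|---|---|
| 104 | 39.39% | No | Excluded | Excluded |
| 105 | 39.77% | No | **Kept** | Excluded |
| 106 | 40.15% | Yes | Kept | Kept |

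The two rules differ only at 105. The shortfall there is 105.6 − 105 = 0.6 of a window, and 0.6 × 5 = 3 minutes.

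**Step 4: see whether another reading gives 105.** With all 288 windows as the denominator, 40% is 0.40 × 288 = 115.2, so at least 116 windows would be needed, and 105/288 is only 36.46%. Rounding 105.6 to the nearest whole number gives 106. Only dropping the decimal gives 105.

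**Step 5: compare with the neighbouring rules.** The actigraphy limits in the same section carry their calculated values into the rule unchanged: 0.70 × 13 h = 9.1 h for the day, and 0.60 × 7 h = 4.2 h for the night. The RMSSD cut-off is the only one that departs from its own derivation.

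**The case against.** The case on the other side is about weight, since the arithmetic is not in dispute.

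- **Size.** One possible count is affected, by 3 minutes of recording. To the nearest whole percent, 39.8% is 40%. The SAP gives no sign that any recording has exactly 105 windows, and no conclusion about RMSSD is likely to depend on it. This stands, and it is why the point is minor.
- **The 40% is a judgement.** The SAP cites no source for it, and nothing suggests that 39.8% represents a day less well than 40.2%. This also stands, but it is a reason to relax the criterion openly. It does not justify a cut-off that contradicts the criterion.
- **The integer rule can be run as written.** Programmers who all follow the final line get the same data set. That is true, but the percentage is stated twice as the requirement, so a check against the criterion would disagree with the program.
- **Displays of all data are also planned.** Most RMSSD summaries and plots are produced with and without the deviators. This helps only in part: the monthly-rate tables (2.115 and 2.126) use quality data alone, as does the statistical analysis.
- **The study is exploratory.** It has no primary endpoint, and correlations are judged by their strength. This lowers the stakes further.

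Two limits on scope are fair. No program is shown, so the inconsistency is between the written criterion and the written cut-off. The note to Table 2.144 refers to three rules although section 7.1.1 gives one for HRV, so the statement that this is the only RMSSD quality rule applies to that section.

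**Conclusion.** The point holds as a minor arithmetic error. The cut-off of fewer than 105 windows contradicts the 40% minimum from which it is derived; the smallest count that satisfies the minimum is 106.

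The misclassification is confined to recordings with exactly 105 windows. Counts of 104 and below are correctly excluded, and counts of 106 and above are correctly kept. LF/HF, actigraphy and speech endpoints are unaffected.

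The conclusion rests only on the SAP's own denominator of 264 and its stated minimum of 40%. How many recordings are affected cannot be determined from the SAP and may be none.

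**What to change.** In section 7.1.1, change the cut-off to exclude a data point with fewer than 106 windows, or write the rule as a proportion: exclude if windows/264 < 0.40. Carry the same wording into the footnote of Table 2.144.

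If 105 was intended, keep it and say that the minimum is approximate, at about 39.8%. Either change brings criterion and cut-off into agreement.

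The cost is one constant in the SAP and the program, or one sentence in the SAP. No further data are needed.

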7.1.2. Planned Statistical Exploratory Analyses

Statistical Analyses
Endpoint(s)

 • Movement/physical activity (Actigraphy) endpoints as measured by the accelerometer device. See Section 2.2 for details. • Heart rate variability endpoints as measured by the electrode device. See Section 2.2 for details. • Speech endpoints. See Section 2.2 for details. • ALSFRS-R total score and ALSFRS-R scores for 4 domains: gross motor activity, fine motor activity, bulbar and respiratory function • FVC
Model Specification

 • Descriptive Statistics 
 ○ Actigraphy 
 ▪ The absolute, change from baseline, and the relative rate of decline for Actigraphy related endpoints will be summarized for each protocol time point using the FAS population ▪ The monthly rate of decline for the whole study period for Actigraphy related endpoints will be summarized using the FAS population ▪ The absolute values over time and relative rate of decline of Actigraphy related endpoints along with the total score over time and relative rate of decline of ALSFRS-R will be plotted against time (X), respectively. ○ Heart Rate Variability 
 ▪ The absolute values, change from baseline, and the relative rate of decline for HRV related endpoints (Mean & Variance for the LF/HF and 24 hours RMSSD analyses) will be summarized for each protocol time point using the FAS population ▪ The monthly rate of decline for the whole study period for HRV related endpoints (Mean & Variance for the LF/HF and 24 hours RMSSD analyses) will be summarized using the FAS population ▪ The absolute values and relative rate of decline of HRV related endpoints (Mean & Variance for the LF/HF and 24 hours RMSSD analyses) along with the absolute and relative rate of decline of ALSFRS-R will be plotted against time (X) respectively. ▪ The Average Value and the raw data of the endpoints from McLaren will be listed ○ Speech assessment

Statistical Analyses

- The absolute values, change from baseline, and the relative rate of decline for Speech related endpoints will be summarized for each protocol time point using the FAS population
- The monthly rate of decline for the whole study period for Speech related endpoints will be summarized using the FAS population
- The absolute values and relative rate of decline of Speech related endpoints along with the absolute values and relative rate of decline of ALSFRS-R total score and FVC values will be plotted against time (X), respectively.

- **Correlation Analysis**

An estimate of the between-subject correlation and the within-subject correlation will be obtained using the method described in [Roy, 2006](#). The between-subject correlation will characterize whether subjects with greater decrease in the endpoint also tend to have the greater change in ALSFRS-R. The within-subject correlation will describe whether a decrease in one endpoint within an individual is associated with a decrease in the other endpoint.

A mixed effect model with the change from baseline in the endpoints and the change from baseline in the ALSFRS-R score as dependent variables will be fitted. An indicator variable to distinguish the two endpoints will be fitted as a fixed effect and a random effect. Other explanatory covariates will be fitted as fixed effects, as appropriate.

The RANDOM and REPEATED statements will be used to specify the structure of the covariance matrix for the two responses. The RANDOM statement will be used to specify an unstructured variance-covariance structure for the two responses. The REPEATED statement will be used to specify the variance covariance matrix for the error terms in the model. The structure of the variance covariance matrix is constructed by taking the Kronecker product of an unstructured matrix, which models the covariance for the two endpoints, with an unstructured or autoregressive (AR (1)) covariance matrix which models the covariance for the 2 repeated measures across visits.

If the data is not sufficient to allow for convergence of the model, then alternative variance covariance matrices may be considered. If convergence of the model parameters still cannot be achieved, the approach by [Bland, 1995](#) will be used to estimate the within subject correlation.

- **Actigraphy**

- The absolute values and change from baseline for the actigraphy endpoints will be analyzed for correlation with absolute values and change from baseline of Total score of ALSFRS-R, respectively.
- The absolute values and change from baseline in the time spent active (day only), Time Spent sedentary not lying (day only), Time Spent Lying (day only), Time Spent Sedentary (day only), Total Activity Score (By 24 Hour and by Day), Maximum Score (By 24 Hour and by Day), Active Periods (Numbers) (day only), Active Periods (Duration) (day only) will be analysed for correlation with the absolute values and change from

Statistical Analyses	

 ○ Heart Rate Variability 
 ▪ The absolute values and change from baseline in the heart rate variability endpoints will be analyzed for correlation with the absolute values and change from baseline in the Total score of ALSFRS-R, respectively. ▪ For the above endpoints analyzed for correlation, scatter plots will be done ○ Speech assessment 
 ▪ The absolute values and change from baseline in the speech endpoints will be analyzed for correlation with the absolute values and change from baseline in the Total ALSFRS-R, respectively. ▪ The absolute values and change from baseline in the speech endpoints will be analyzed for correlation with the absolute values and change from baseline of bulbar domain and respiratory domain of ALSFRS-R, respectively. ▪ The absolute values and change from baseline in the speech endpoints will be analyzed for correlation with the absolute values and change from baseline in the FVC, respectively. 	
baseline to the-gross motor domain and fine motor domain of ALSFRS-R, respectively.
 
For the above endpoints analyzed for correlation, scatter plots will be done
 
The correlation analysis will be performed on both non normalized and normalized data. Only the quality data (i.e. the data without the data quality deviators as defined in Section 7.1.1) will be used for the statistical analysis.
 
Only the quality data will be used for the statistical analysis.
 
Only the quality data will be used for the statistical analysis.

Model Results Presentation	

 ● Descriptive Statistics 
 ○ Data listings ○ Summary tables ○ Visualization graphs ● Correlation Analysis 
 ○ Result tables ○ Visualization graphs 	

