9.4.3. Exploratory

ALSFRS-R Total Score

The ALS functional rating scale – revised (ALSFRS-R) assesses the functioning of ALS subjects across 4 domains: gross motor activity, fine motor activity, bulbar and respiratory function. The ALSFRS-R [Cedarbaum, 1999] consists of 12 questions each of which are scored on a 5-point scale from 0-4, where 4 is the best possible outcome and 0 is the worst.
 
The total score will be calculated by summing responses to each of the 12 individual questions. The maximum total score is therefore 48, lower scores indicate worse functioning. If there are any missing questions, then the total score will be set to missing.
 
ALSFRS will be grouped to four different domains: Fine motor, Gross motor, Respiratory and Bulbar Domain [Cedarbaum, 1999]

FVC

FVC is a measure of respiratory function and is the volume of air that can forcibly be blown out after a single, full breath. FVC is a sensitive measure of ALS disease progression, is used as a standard test for ALS management, and is recommended as a secondary outcome measure in ALS clinical trials [Cudkowicz, 2004; Czaplinski, 2006; Clavelou, 2013].
 
FVC will be performed by experienced site personnel according to local protocol using a calibrated spirometer. Every effort should be made to have the same individual perform the FVC for a given subject throughout the study. For each time point, the best FVC result (in litres) will be recorded in the eCRF.

Relative Rate of Decline and Monthly Rate of Decline (Slope)

Relative Rate of Decline = $\frac{\text{Value at a time point} - \text{Value at the Baseline}}{\text{Value at the Baseline}}$
 
 $\frac{\text{Monthly rate of decline at each visit} = \frac{\text{Change from baseline of the endpoint at each post-baseline visit}}{\text{Study day}/30.4}}$ 
 
Monthly Rate of Decline= Average of Monthly Rate of Decline at each visit and is populated only for the last visit.
 
For Monthly Rate of Decline, if an assessment took place over a number of consecutive days then the average of that will be taken and the recent visit (last time point) will be considered to calculate study day.

Actigraphy

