9.9. Appendix 9: Model Checking and Diagnostics for Statistical Analyses

9.9.1. Statistical Analysis Assumptions

Endpoint(s)	
 • Actigraphy, HRV and Speech
Analysis	
 • MMRM

 • Model assumptions will be applied, but appropriate adjustments maybe made based on the data. • The Kenward and Roger method for approximating the denominator degrees of freedom and correcting for bias in the estimated variance-covariance of the fixed effects will be used. • An unstructured covariance structure for the R matrix will be used by specifying 'type=UN' on the REPEATED line. 
 ○ In the event that this model fails to converge, alternative correlation structures may be considered such as CSH or CS. ○ Akaike's Information Criteria (AIC) will be used to assist with the selection of covariance structure. • Distributional assumptions underlying the model used for analysis will be examined by obtaining a normal probability plot of the residuals and a plot of the residuals versus the fitted values (i.e. checking the normality assumption and constant variance assumption of the model respectively) to gain confidence that the model assumptions are reasonable. • If there are any departures from the distributional assumptions, alternative models will be explored using appropriate transformed data. 	

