2.55.	FAS	EFF_T1	Summary of Monthly Rate of Decline of Maximum Score (1 min – 24 Hour Window) (Quality data)	Same as above	SAC
2.56.	FAS	EFF_T1	Summary of Active Periods (Numbers) (All data)	For day and night active periods separately & for each category (> 1 to <= 2 minutes, > 2 to <= 5 minutes etc. etc): Categorise into Day and Night Time Modify EFF_T1 as: Add n (%) instead of statistics Add columns for categories	SAC
2.57.	FAS	EFF_T1	Summary of Active Periods (Numbers) (Quality data)	Same as Above	SAC

Efficacy: Tables					
No.	Population	IDSL / TST ID / Example Shell	Title	Programming Notes	Deliverable [Priority]
2.58.	FAS	EFF_T1	Summary of Active Periods (Duration) (All data)	Categorise into Day and Night Time	SAC
2.59.	FAS	EFF_T1	Summary of Active Periods (Duration) (Quality data)	Same as Above	SAC
2.60.	FAS	EFF_T1	Summary of Change from Baseline of Active Periods (Duration) (All Data)	Same as Above	SAC
2.61.	FAS	EFF_T1	Summary of Active Change from Baseline of Periods (Duration) (Quality data)	Same as Above	SAC
2.62.	FAS	EFF_T1	Summary of Relative Rate of Decline of Active Periods (Duration) (All data)	Same as Above	SAC
2.63.	FAS	EFF_T1	Summary of Relative Rate of Decline of Active Periods (Duration) (Quality data)	Same as Above	SAC
2.64.	FAS	EFF_T1	Summary of Monthly Rate of Decline of Active Periods (Duration) (Quality data)	Same as Above	SAC
2.65.	FAS	EFF_T3	Statistical Analysis of Relationship between Absolute Values of Actigraphy endpoints and Absolute Value of Total ALSFRS-R		SAC
2.66.	FAS	EFF_T3	Statistical Analysis of Relationship between Change from Baseline of Actigraphy endpoints and Change from Baseline of Total ALSFRS-R		SAC
2.67.	FAS	EFF_T3	Statistical Analysis of Relationship between Slope of Actigraphy endpoints and Slope of Total ALSFRS-R		SAC

Efficacy: Tables					
No.	Population	IDSL / TST ID / Example Shell	Title	Programming Notes	Deliverable [Priority]
2.68.	FAS	EFF_T3	Statistical Analysis of Relationship between Absolute Values of Actigraphy endpoints and Absolute Value of gross motor domain of ALSFRS-R		SAC
2.69.	FAS	EFF_T3	Statistical Analysis of Relationship between Change from Baseline of Actigraphy endpoints and Change from Baseline of gross motor domain of ALSFRS-R		SAC
2.70.	FAS	EFF_T3	Statistical Analysis of Relationship between Slope of Actigraphy endpoints and Slope of gross motor domain of ALSFRS-R		SAC

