2.71.	FAS	EFF_T3	Statistical Analysis of Relationship between Absolute Values of Actigraphy endpoints and Absolute Value of fine motor domain of ALSFRS-R		SAC
2.72.	FAS	EFF_T3	Statistical Analysis of Relationship between Change from Baseline of Actigraphy endpoints and Change from Baseline of fine motor domain of ALSFRS-R		SAC
2.73.	FAS	EFF_T3	Statistical Analysis of Relationship between Slope of Actigraphy endpoints and Slope of fine motor domain of ALSFRS-R		SAC
Night Time Rest Endpoints					
2.74.	FAS	EFF_T1	Summary of Number Night Time Movement (All data)		SAC
2.75.	FAS	EFF_T1	Summary of Number Night Time Movement (Quality data)		SAC
2.76.	FAS	EFF_T1	Summary of Change from Baseline of Number Night Time Movement (All data)		SAC

CONFIDENTIAL

201283

Efficacy: Tables					
No.	Population	IDSL / TST ID / Example Shell	Title	Programming Notes	Deliverable [Priority]
2.77.	FAS	EFF_T1	Summary of Change from Baseline of Number Night Time Movement (Quality data)		SAC
2.78.	FAS	EFF_T1	Summary of Relative Rate of Decline of Number Night Time Movement (All data)		SAC
2.79.	FAS	EFF_T1	Summary of Relative Rate of Decline of Number Night Time Movement (Quality Data ta)		SAC
2.80.	FAS	EFF_T1	Summary of Monthly Rate of Decline of Number Night Time Movement (Quality data)		SAC
2.81.	FAS	EFF_T1	Summary of Percent Time Night-time Rest Efficiency (All data)		SAC
2.82.	FAS	EFF_T1	Summary of Percent Time Night-time Rest Efficiency (Quality data)		SAC
2.83.	FAS	EFF_T1	Summary of Change from Baseline of Percent Time Night-time Rest Efficiency (All data)		SAC
2.84.	FAS	EFF_T1	Summary of Change from Baseline of Percent Time Night-time Rest Efficiency (Quality data)		SAC
2.85.	FAS	EFF_T1	Summary of Relative Rate of Decline of Percent Time Night-time Rest Efficiency (All data)		SAC

CONFIDENTIAL

201283

Efficacy: Tables					
No.	Population	IDSL / TST ID / Example Shell	Title	Programming Notes	Deliverable [Priority]
2.86.	FAS	EFF_T1	Summary of Relative Rate of Decline of Percent Time Night-time Rest Efficiency (Quality data)		SAC
2.87.	FAS	EFF_T1	Summary of Monthly Rate of Decline of Percent Time Night-time Rest Efficiency (Quality data)		SAC
2.88.	FAS	EFF_T1	Summary of Rest Fragmentation Index (All data)		SAC
2.89.	FAS	EFF_T1	Summary of Rest Fragmentation Index (Quality data)		SAC
2.90.	FAS	EFF_T1	Summary of Change from Baseline of Rest Fragmentation Index (All data)		SAC
2.91.	FAS	EFF_T1	Summary of Change from Baseline of Rest Fragmentation Index (Quality data)		SAC

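### SAP Section 7.1.2 permits an unstructured visit matrix alongside an unstructured RANDOM matrix; under that option the between-subject correlation is not identified

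*SAP*

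**What the plan says.** Under Correlation Analysis, SAP Section 7.1.2 promises both a between-subject and a within-subject correlation for each pair of endpoints. The endpoint indicator enters as a fixed and as a random effect. For the random part, "The RANDOM statement will be used to specify an unstructured variance-covariance structure for the two responses". The error part is a Kronecker product of an unstructured endpoint matrix "with an unstructured or autoregressive (AR (1)) covariance matrix which models the covariance for the 2 repeated measures across visits". No rule chooses between the two visit structures.

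The safeguard is for non-convergence: "If the data is not sufficient to allow for convergence of the model, then alternative variance covariance matrices may be considered". If that also fails, a cited method for repeated observations supplies the within-subject correlation only.

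Section 9.9.1, headed for the MMRM, says that "alternative correlation structures may be considered such as CSH or CS" if that model fails to converge, and that AIC "will be used to assist with the selection of covariance structure". Section 9.8 bases conclusions on how strong the correlation coefficients are and makes no multiplicity adjustment.

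**The concern.** A random intercept per endpoint adds the same constant block to every pair of visits. An unstructured visit matrix can absorb a constant of that kind too. When both are in the model, nothing in the data says how much of the constant covariance belongs to each. The between-subject correlation depends on that split.

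This coefficient is one of the two quantities the model exists to estimate, and Section 9.8 judges endpoints by its size. Under the unstructured option, the printed value would depend on where the optimiser stopped. The reader of the table would have no sign of this.

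**Working it through.** The plan gives no figure to reproduce here, so the check is of the model itself.

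**Inputs from the SAP.** The model is as described in Section 7.1.2. Visit counts come from the Time & Events table in Section 9.1.1. Speech and FVC have 4 post-baseline clinic visits (5 with baseline). ALSFRS-R has 5 clinic and 8 telephone times, so 13 with baseline and 12 without. I read the 2 in the quoted sentence as the two endpoints, since the schedule has far more than two visits.

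**Step 1: the covariance.** Let G be the RANDOM matrix, S the endpoint matrix, V the visit matrix and J the all-ones matrix. The marginal covariance is

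S⊗V + G⊗J.

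Replace G by G − cS and V by V + cJ. The result is S⊗V + cS⊗J + G⊗J − cS⊗J, which is the same matrix. If V is unstructured, V + cJ is also an allowed V. The same holds for every sub-block, so missing visits, covariates, REML or more subjects do not remove the problem. S keeps its correlation, so the within-subject coefficient is safe. The between-subject correlation from G changes with c unless G is exactly proportional to S.

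**Step 2: parameter counts.** Fix V₁₁ = 1 to set the scale. With t visits the unstructured option has 3 + 3 + t(t+1)/2 − 1 parameters. Numerical ranks of the Jacobian (identified / fitted) are:

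| Visit factor | 4 visits | 5 visits | 12 visits | 13 visits |
|---|---|---|---|---|
| Unstructured | 14/15 | 19/20 | 82/83 | 95/96 |
| CS | 6/7 | 6/7 | 6/7 | 6/7 |
| AR(1) | 7/7 | 7/7 | 7/7 | 7/7 |

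CS fails because V + cJ is still CS after rescaling. CSH contains CS, so it is also one short when the visit variances are equal.

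**Step 3: why AR(1) works.** For V + cJ to be AR(1) after rescaling, the lag-1 and lag-2 entries must satisfy (ρ + c)² = (ρ² + c)(1 + c). This reduces to c(1 − ρ)² = 0, so c = 0. The lag-2 entry needs three visits; with two visits AR(1) fails as well (6/7).

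**Step 4: how wide the range is.** Assumed inputs, not from the SAP: between-subject 0.60, within-subject 0.10, visit correlation AR(1) with ρ = 0.7, and unit variances in G and S.

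- The lower end is at c = −1/(1′V⁻¹1) = −(1 + ρ)/(t − (t − 2)ρ).
  - 4 visits: 1.7/2.6 = 0.654, giving (0.60 + 0.10 × 0.654)/(1 + 0.654) = 0.40.
  - 12 visits: 1.7/5.0 = 0.340, giving (0.60 + 0.034)/1.340 = 0.47.
- The upper end is at c equal to the smallest generalised eigenvalue of (G, S), 0.4/0.9 = 0.444. This gives (0.60 − 0.044)/(1 − 0.444) = 1.00.
- If the variances in S are only 0.1 of those in G, the range narrows at the lower end, to 0.57–1.00 (4 visits) and 0.58–1.00 (12 visits).

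**Step 5: likelihood check.** One simulated data set was used with 4 visits, 30 subjects, between 0.60, within 0.20 and visit correlation 0.5, all assumed. Between-subject values of 0.9992, 0.7333, 0.6000, 0.5200 and 0.4668 all gave a log-likelihood of −103.752060. The within-subject value stayed at 0.2000.

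**The case against.** The strongest reply is that the defect is confined. AR(1) stands in the same sentence and is identified at the planned visit counts, the within-subject coefficient is untouched, and the study has no primary endpoint and no numeric threshold. All of that stands and limits the impact.

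It can also be said that the SAP never states that the between-subject coefficient comes from the RANDOM matrix; it defers to a cited paper that is not at hand. This is fair. G is the natural reading, since REPEATED is said to model the error terms, but it is a reading.

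Third, the practical harm is argued and not shown. SAS was not run and may warn of a singular Hessian. A large unstructured fit in few subjects may simply fail to converge and so reach the existing fallback. That is possible. But a fit can also converge on a flat ridge, and the plan does not make a warning a trigger. AIC cannot separate points on the ridge, since they have the same likelihood, and its sentence is written for the MMRM.

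A reader might infer that the whole correlation analysis is invalid, or that the reported coefficient is bound to be arbitrary. The SAP does not support either: one of its two named visit structures is sound, and it does not say which will be used. Nor should CSH be taken as a safe replacement without qualification, given its failure when visit variances are equal.

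**Conclusion.** The point holds in a limited form. Section 7.1.2 permits a model in which the between-subject correlation, taken from the RANDOM matrix, has no unique value unless G happens to be proportional to S. The one-rank shortfall is algebraic and does not depend on sample size or on any assumed variance. The ranges 0.40–1.00 and 0.47–1.00 do depend on the assumed inputs; they are admissible limits, not likely estimates.

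The impact is modest but worth correcting before the analysis. An exploratory aim can excuse an imprecise coefficient, but not one that the data cannot determine.

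**What to change.** In Section 7.1.2:

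- Delete the unstructured alternative for the visit factor, so that UN@AR(1) is used with the RANDOM statement for endpoint pairs with at least three usable visits.
- State that unstructured and CS visit factors are not combined with the RANDOM statement, including when alternative matrices are considered after a failed fit.
- Treat a singular Hessian, like non-convergence, as a trigger for the fallback.
- Show the covariance structure used beside each reported coefficient.

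The cost is a change of SAP wording and one covariance option in the program; no new data are needed. The downside is that AR(1) assumes constant residual variance and a single autocorrelation. Change-from-baseline data may violate both, so residual variance by visit should be checked. Where the trigger leads to the last fallback, only a within-subject coefficient will be available, as the plan already implies.
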